6 STUDY PROCEDURES

6.1 Schedule of Evaluations

Measures	Test/Type	Visit	Pre-Intervention	During Intervention	Post-Intervention
			Baseline week 0	weeks 1-12	Post week 12-16
Verbal consent	Consent	Phone ✓			
Demographic/Health Screen	Screen	Phone ✓			
Memory Impairment Screen	Screen	Phone ✓			
AD-8 Dementia Screening Interview	Screen	Phone ✓			
Handedness	Screen	Phone ✓			
MRI safety (verbal)	Screen	Phone ✓			
Informed Consent	Consent	Study Visit	✓		
MRI safety (paper)	Screen	Study Visit	✓		✓
Baseline Medical history	Survey	Study Visit	✓		
Sensory Screen	Physical	Study Visit	✓		
Medications	Survey	Study Visit	✓		
Height/Weight/BMI	Physical	Study Visit	✓		✓
Blood Pressure	Physical	Study Visit	✓		✓
SPPB	Physical/Gait	Study Visit	✓		✓
Maze	Cognitive/Gait	Study Visit	✓		✓
Berg Balance Scale	Physical/Gait	Study Visit	✓		✓
Unipedal Stance	Physical/Gait	Study Visit	✓		✓
Stair climbing	Physical/Gait	Study Visit	✓		✓
Grip Strength	Physical/Gait	Study Visit	✓		✓
WRAT & WTAR	Cognitive	Study Visit	✓		✓
RBANS figure copy & delay	Cognitive	Study Visit	✓		✓
Free Cued Serial Recall Test	Cognitive	Study Visit	✓		✓
Falls Questions	Survey	Study Visit/Phone	✓	✓	✓
Falls Efficacy Scale	Survey	Study Visit	✓		✓
Duke Activity Status Index	Survey	Study Visit	✓		✓
Trails A & B	Cognitive	Study Visit	✓		✓
Control Oral Word Association Test	Cognitive	Study Visit	✓		✓

Semantic Fluency	Cognitive	Study Visit	✓	✓
General Mobility Questionnaire	Survey	Study Visit	✓	✓
Geriatric Depression Scale (GDS-30)	Survey	Study Visit	✓	✓
Instrumental ADL Questionnaire	Survey	Study Visit	✓	✓
Flanker Interference	Cognitive	Study Visit	✓	✓
WAIS Digit Symbol Substitution Test	Cognitive	Study Visit	✓	✓
Stroop Interference	Cognitive	Study Visit	✓	✓
Activity Balance Confidence Scale	Survey	Study Visit	✓	✓
SF-12	Survey	Study Visit	✓	✓
CHAMPS	Survey	Study Visit/Phone	✓	✓
Letter Number Sequencing	Cognitive	Study Visit	✓	✓
Social Network Index	Survey	Study Visit	✓	✓
Beck Anxiety Inventory	Survey	Study Visit	✓	✓
MOS Social Support Survey	Survey	Study Visit	✓	✓
Gait Rite	Physical/Gait	Study Visit	✓	✓
Imagery Protocol		Study Visit	✓	✓

6.2 Description of Evaluations

6.2.1 Screening Evaluation

Consenting Procedure

A letter explaining our study will be sent and followed by a telephone call a few days later. Those expressing interest will be screened using a structured telephone interview to obtain verbal consent. Potential recruits will then be screened over the phone, and those who meet eligibility criteria will be scheduled for their first study visit. They will also be told that they will receive a phone call reminder the evening before their appointment. Written consent will occur in our research center and conducted by trained RAs. On arrival, potential participants will review study information and sign consent. Consenting will take place prior to any assessments.

All consent forms will be stored in a locked file with other study documents and records. See approved Consent form in Appendix I.

Screening

Potential recruits who meet eligibility criteria on the telephone are invited to schedule their first study session, and are told that they will receive a phone call reminder the evening before the appointment.

Telephone screening: A letter explaining our study will be sent, followed by a telephone call a few days later. Those expressing interest will be screened over the phone prior to enrollment. Telephone screening responses will also be reviewed and/or repeated (e.g. MRI safety) during the first study session to ensure eligibility prior to other study procedures. Inclusion criteria are: 1) age 65-85 years old 2) able to speak English at a level sufficient to undergo study procedures, and 3) plan to be in the area for the next 3 months. Exclusion criteria are: 1) Presence of dementia (telephone-based

memory impairment screen MIS < 5 or AD-8 score >, 2) Presence of gait disorder (e.g. neuropathy), progressive neurodegenerative disease (e.g. Parkinson's disease) or major psychiatric disorder (e.g. Schizophrenia), 3) MRI contraindication (e.g. pacemaker), 4) participation in other interventional or observational study during the study period, and 5) any medical condition or chronic medication use (e.g. neuroleptics) that will compromise safety or affect cognitive functioning.

6.2.2 Enrollment, Baseline, and Randomization

Enrollment

The enrollment date is defined as the date that the participants are randomized into either the motor imagery or visual imagery intervention, after they have met all screening criteria and agreed to participate.

Baseline Assessments

For participants who have successfully been screened for eligibility, baseline assessments are performed during their first study session.

Randomization

Randomization will be determined after completion of the baseline assessments. Initiation of the study intervention will take place in the week following the baseline assessment visit.

6.2.3 Follow-up Visits

Post intervention follow-up assessments will occur within 4 weeks of the completion of the intervention. In addition adverse events will be evaluated over the phone throughout the intervention and at the post-intervention visits. A 4-week window will be allowed for each of the post-intervention assessments.

6.2.4 Completion/Final Evaluation

Assessments to be completed at the final visit (12 months post-intervention) are listed in Table 5.1.

Losses to follow-up can be classified into non-informative (missing at random (MAR)) and informative censoring (drop out depends on the unobserved outcomes). No adjustment is necessary for non-informative censoring. However, for informative censoring, parameter estimates and resulting tests on hypotheses will be biased without further adjustment. The best way to handle missing data is to avoid it. However, we recognize that despite all our efforts there will be missing data.

Dropouts: We will follow-up with participants who dropped out of the study to determine both their mobility status and reasons for withdrawal. The research team will adjudicate events such as mobility disability in subjects who drop out based on medical interviews, contact interviews, and home assessments as required. Utilization of the telephone based

questionnaire to account for possible non-random drop-out will be administered. If the participant is acutely ill, is in the hospital, or has a temporary condition that interferes with walking (e.g. ankle sprain), we will attempt to complete the assessment at another time.

We also propose intention to treat (ITT) analysis, which includes all randomized participants in the groups assigned, regardless of their adherence with the entry criteria, whether motor imagery was received, and subsequent withdrawal or deviation from the protocol. ITT analysis is pragmatic because it admits noncompliance and protocol deviations, and gives an unbiased estimate of the intervention effect. Handling missing data is a major issue in ITT, and is dealt with by imputation or sensitivity analysis. Our statistician, [name], is very experienced in these methods.

A rich set of telephone-based information will be collected even for those subjects who may drop out. We will utilize this auxiliary information to assess the MAR assumption and combine it into the main model through joint modeling and multiple imputation approaches. [name] has applied these approaches to eliminate or reduce bias in presence of informative censoring in our other aging studies.

7 **SAFETY ASSESSMENTS**

7.1 **Specification of Safety Parameters**

The research staff and investigators will be present during all testing. All questionnaire completion will be done at a slow enough pace so as not to tire individuals. If subjects express physical or mental tiredness or discomfort during any of the assessments or training procedures, the procedure will be terminated immediately. Drs. [name] and [name] will be available onsite or cell at all times to address any safety concerns or clinical issues during the interventions.

All abnormal findings from the clinical, mobility, neuroimaging, and neuropsychological assessments done on baseline, screening visits, and post-intervention visits will be documented and reviewed by the DSMB chair. Periodic audits from the Albert Einstein College of Medicine IRB ensure compliance with confidentiality guidelines and adverse events monitoring.

7.2 **Methods and Timing for Assessing, Recording, and Analyzing Safety Parameters**

Answering health questionnaires and mental state examinations involve minimal psychological, social, or other risks. We do not expect any serious adverse events during these non-invasive tests and training programs of attention and executive function. The motor imagery and visual imagery interventions involve mental but no physical effort by the participants. Some people are bothered by feelings of confinement (claustrophobia), and by the noise made during MRI. Participants will be asked to wear earplugs or earphones while in the MRI machine. They may not participate in this study if they have a pacemaker, an implanted defibrillator or certain other implanted electronic or metallic devices.

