9.2 Sample Size and Randomization

The primary hypothesis examines change in gait speed (during NPW and WWT conditions). Setting an alpha level of .05, power of .80 and a medium effect size of defined as $f=.25$, the necessary sample size for detecting an interaction between time of test (pre and post), trial type (W or WWT) and imagery condition (Imagined gait or AC) is $n = 34$. Thus, our study completion goal of $n = 48$ (58 enrolled; 48 completed) is sufficient to detect our effects of interest and account for the 18% attrition rate expected during the study period (as observed in our previous studies (64)).

To detect a BOLD signal change at the individual subject level (i.e. first-level time-series modeling using SPM) at $p < 0.001$, a percent signal change of 0.34% is required using a published method and estimate of noise at a magnet strength of 3.0 Tesla (65). Based on this estimate, to detect a difference in contrast values between groups (i.e. second level analyses using SPM) at $p < 0.001$ and a power of at least .80, where the mean of one group's signal change is 50% of the other, 16 subjects per group are required. Thus, our study completion goal of $n = 48$ (24 in each condition) is sufficient to detect a main effect of imagery condition (imagined gait vs. AC) and leave room for the detection of interactions

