9.4 Data Analyses

9.4.1 Primary outcome.

To examine gait speed during W and WWT we will use repeated-measures analyses that include time of test (pre and post), and trial type (W or WWT) as within subjects factors, and imagery condition (imagined gait or AC) as the between-subjects factor. Consideration of these analyses will focus on the three-way interaction between time of test, trial type, and imagery condition.

9.4.2 Secondary and tertiary outcomes.

Similar repeated-measures analyses will be used for our secondary outcomes measures/additional EF measures: Trail Making Test, the Letter Number Sequencing Test, the Stroop Color and Word Test, and the Flanker Interference Task. These measures include the time to complete Trails B corrected for Trails A from the Trail Making Test (Trails B-A), the raw score from the letter-number sequencing task WAIS-III, the raw response time to Color-Word (incongruent) trials corrected for Color (congruent) trials from the Stroop Color and Word Test (i.e., Stroop Interference) and the flanker interference response time measure (incongruent-congruent trials) from the Flankers interference task. Although three of these four measures are difference scores, our analyses will be completed on raw scores in order to maximize power. More specifically, for these measures we will use repeated-measures analyses that included time of test (pre and post) and trial type as within subjects factors, and imagery condition (imagined gait or AC) as the between-subjects factor. Trial type for the Trail Making Test will be Trails A and Trails B. Trial Type for the Stroop Color and Word Test will be congruent trials and incongruent trials. Finally, trial type for the Flanker task will be congruous and incongruous trials. Consideration of these analyses will focus on the three-way interaction between time of test, trial type, and condition. Analyses will focus on the primary outcome variables during training and to the end of training period.

All behavioral analyses will be corrected for multiple comparisons using the Bonferroni correction.

We will use a whole-brain multivariate Ordinal Trend Covariance Analysis (OrT-CVA) to analyze the BOLD signal during imagined walking and walking while talking (66, 67). This is because we are interested in determining how the use of the entire locomotion and executive

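### Section 6.2.4 says dropout that is missing at random needs no adjustment, but that is true only for certain analyses, and Section 9.4 names none of them

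*Combined protocol and SAP*

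**What the plan says.** Section 6.2.4 sorts dropout into two kinds: "Losses to follow-up can be classified into non-informative (missing at random (MAR)) and informative censoring". For the first kind it states "No adjustment is necessary for non-informative censoring", and it warns of bias without adjustment only for the second. The same section then promises an intention-to-treat (ITT) analysis of everyone randomised, with missing data handled by imputation or sensitivity analysis. It also plans to use telephone data to "assess the MAR assumption and combine it into the main model through joint modeling and multiple imputation approaches". Section 8 repeats these commitments.

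Section 9.4.1 gives the primary analysis of gait speed: "we will use repeated-measures analyses that include time of test (pre and post") and trial type (walking, W, or walking while talking, WWT) as within-subject factors, with imagery arm between subjects. The focus is the three-way interaction. The closing paragraph of Section 9.4 adds age, sex and education as covariates. Section 9.4 names no analysis set, no mixed or likelihood model, no imputation, and no rule for a missing post visit.

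Two other places bear on who is analysed. Section 5.4 removes from the main analyses anyone who misses six sessions. Section 9.2 rests the sample size on 48 completers out of 58 enrolled, to "account for the 18% attrition rate expected during the study period".

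**The concern.** MAR does not by itself make missing data harmless. It means that dropout depends only on observed quantities, and the analysis must then use those quantities. A likelihood model fitted to all observed data does so, as does multiple imputation. An analysis of raw change among people with both visits does not, unless dropout is unrelated to baseline or related to it in the same way in both arms.

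The plan has one post-intervention visit. A conventional repeated-measures ANOVA needs both visits and tests raw change. The sentence in 6.2.4 would license it, and the completer-based sample size and the six-session exclusion fit it. An analyst who followed Sections 5.4, 9.2 and 9.4 could report a completers' contrast. Another who followed Sections 6.2.4 and 8 could report an imputed ITT estimate. Both could claim to have followed the plan, and the choice could be made after seeing the data.

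**Working it through.** **Inputs from the documents.** f = 0.25, alpha 0.05, power 0.80, required N = 34, 58 enrolled and 48 completed, 18% attrition (Section 9.2); two outcome visits (Section 2.1); WWT test-retest r = 0.935 in 31 subjects, interval not stated (Section 9.1.1).

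**Assumed, because the documents do not give them.** Pre-post correlation ρ from 0.5 to 0.935; equal SDs; W-WWT correlation c from 0.6 to 0.8; logistic dropout on standardised baseline with a log-odds slope of 1 per SD, calibrated to 18% in each arm; true effect zero.

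**The plan's own figures.** For a two-group interaction with m = 2 measurements, λ = f²·N·m/(1 − ρ). With ρ = 0.5, λ = 0.0625 × 34 × 2/0.5 = 8.5 on 1 and 32 df, and power is 0.807, so N = 34 is reproduced. For attrition, 48/(1 − 0.18) = 58.5, or 59 against the stated 58. About ten people (58 − 48) are expected to have no post visit.

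**Bias for one speed outcome.** If lower baseline makes dropout more likely, completers have a higher mean baseline than those randomised. Integrating the logistic model gives a shift δ = 0.157 SD. Given baseline b, expected change is (ρ − 1)b, so the size of the bias in the completers' contrast is (1 − ρ) × (difference in δ between arms). That difference is 0 if both arms share the pattern, 0.157 if only one arm has it, and 0.314 if the patterns are opposite.

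| ρ | One arm only | Opposite patterns |
|---|---|---|
| 0.5 | 0.5 × 0.157 = 0.08 | 0.5 × 0.314 = 0.16 |
| 0.7 | 0.3 × 0.157 = 0.05 | 0.3 × 0.314 = 0.09 |
| 0.8 | 0.2 × 0.157 = 0.03 | 0.2 × 0.314 = 0.06 |
| 0.935 | 0.065 × 0.157 = 0.01 | 0.065 × 0.314 = 0.02 |

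Simulation agrees where run: 0.077 and 0.160 at ρ = 0.5; 0.046 and 0.094 at ρ = 0.7. A slope of 2 raises the ρ = 0.5 figures to about 0.12 and 0.23. The estimator that conditions on baseline was within 0.005 of zero throughout.

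**Type I error, 29 randomised per arm, slopes 1 to 2, ρ from 0.5 to 0.9.** About 0.05 with a shared pattern, 0.05 to 0.07 with one arm only, and 0.06 to 0.13 with opposite patterns.

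**Against sampling error.** With 24 per arm, the standard error of the change contrast is √(2(1 − ρ)) × √(2/24). At ρ = 0.5 this is 0.289, so the bias is 0.08/0.289 = 0.3 to 0.16/0.289 = 0.6 of a standard error. At ρ = 0.935 it is 0.104, so the bias is 0.1 to 0.2 of a standard error.

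**Bias for the planned three-way contrast.** The outcome is now change in D = WWT − W.

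- Dropout depends on average baseline speed: with equal SDs this is uncorrelated with D, so the bias is about 0.
- Dropout depends on W alone: the bias is (1 − ρ)(1 − c) × the difference in δ. At ρ = 0.5 it runs from 0.5 × 0.2 × 0.157 = 0.02 to 0.5 × 0.4 × 0.314 = 0.06 SD of speed. At ρ = 0.935 it is below 0.01.
- Dropout depends on D itself: the table applies in SDs of D, with ρ the pre-post correlation of D, so up to 0.16 at 0.5.

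D is less stable than either speed. If both speeds had reliability 0.935, D would have pre-post correlation (0.935 − c)/(1 − c), which is 0.335/0.4 = 0.84 at c = 0.6 and 0.135/0.2 = 0.68 at c = 0.8. In the third case the bias would then lie between about 0.03 and 0.10 SD of D.

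**The case against.** The strongest reply is that the plan never commits to the analysis being criticised. Section 9.4 does not mention ANOVA or completers. The term repeated-measures analyses covers a likelihood mixed model, for which the sentence in 6.2.4 is ordinary shorthand and correct. Imputation is promised in the same section as that sentence and tied to the main model. This stands. A reader might infer that the plan prescribes a completers-only analysis, or that it omits imputation. The documents support neither, and the sentence is unqualified rather than false in every use.

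The size is also open to challenge. MAR alone does not bias the arm contrast, and nothing in the documents suggests that two phone-based imagery programmes of equal length would lose different kinds of people. At the only retest correlation given for a gait-speed outcome, the bias is small. A reader might take 0.16 SD as the expected error in the primary result. It is the figure for opposite dropout patterns at a correlation of 0.5, and it applies to the three-way contrast only if dropout tracks D. The 0.935 is not fully reassuring either, because it describes one speed and the planned contrast concerns a difference.

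A reader might also conclude that planning to assess MAR is pointless. Observed data cannot verify MAR for the missing gait speeds. The follow-up of dropouts for mobility status and reasons for withdrawal does bear on how plausible it is.

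The reply does not remove the conflict. Section 9.4 does not say which method applies, and the six-session exclusion in Section 5.4 contradicts the ITT text directly.

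**Conclusion.** The point holds in limited form and should be fixed before analysis. The rule in 6.2.4 is stated without the condition that makes it true, and Section 9.4 does not supply that condition. Sections 5.4, 6.2.4, 8 and 9.4 do not agree on who is analysed or how missing post visits are handled. The consequence ranges from nothing to moderate. It is about zero with a shared dropout pattern. Otherwise it is 0.01 to 0.16 SD for one speed, and about 0 to 0.06 SD for the three-way contrast unless dropout tracks the WWT-minus-W difference. These sizes rest on 18% dropout, a slope of 1 per SD, arm-specific dropout patterns and assumed correlations. They also require the completers' reading of Section 9.4, which the plan does not state.

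**What to change.** - **Section 6.2.4.** Qualify the sentence, for example: *Under MAR no further adjustment is needed when the likelihood-based or multiply imputed model of Section 9.4.1 is used.* Say that the telephone data inform the plausibility of MAR, in place of assessing it.
- **Section 9.4.1.** State that the primary analysis includes all randomised participants through a likelihood-based repeated-measures model, or ANCOVA with multiple imputation. Include baseline W and WWT speed, arm, age, sex and education. Bring in the telephone data through the joint or imputation model; those collected after randomisation should not be ordinary covariates in the treatment comparison.
- **Analysis set.** Reconcile Sections 5.4, 6.2.4, 8 and 9.4. If the analysis without participants who miss six sessions is kept, label it as supplementary to the ITT analysis.
- **Optional.** A delta-adjusted analysis would be one concrete form of the sensitivity analysis already promised.

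The cost is wording and a modest amount of analysis, with no new data or visits.

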7.3 Adverse Events and Serious Adverse Events

An **adverse event (AE)** is defined as any untoward or unfavorable medical occurrence in a human subject, including any abnormal sign (for example, abnormal physical exam), symptom, or disease, temporally associated with the subject's participation in the research, whether or not considered related to the subject's participation in the research. Adverse Events encompass both physical and/or psychological harms. AEs will be documented on forms (See Appendix II).

A **serious adverse event (SAE)** is defined as any untoward medical occurrence that results in death, is life threatening, requires inpatient hospitalization or prolongation of existing hospitalization, results in persistent or significant disability/incapacity, or is a congenital anomaly. SAEs will be documented on SAE forms (Appendix II).

Unanticipated Problem (UP): Any event, deviation, or problem, that is unexpected; AND possibly, probably or definitely related to study participation; AND serious.

- a. Unexpected: An event can be categorized as unexpected if it occurs in one or more subjects participating in a research protocol; and the nature, severity, or frequency of which is not consistent with either:
 - i. The known or foreseeable risk of adverse events associated with the procedures involved in the research that are described in protocol-related documents such as: the IRB-approved research protocol; any applicable investigator brochure; the current IRB-approved informed consent document; or other relevant sources of information, such as product labeling and package inserts; or
 - ii. The expected natural progression of any underlying disease, disorder, or condition of the subject(s) experiencing the adverse event and the subject's predisposing risk factor profile for the adverse event.
- b. Serious: An adverse event or suspected adverse reaction is considered "serious" if, in the view of either the investigator or sponsor, it results in any of the following outcomes:
 - i. death,
 - ii. a life-threatening adverse reaction,
 - i. inpatient hospitalization or prolongation of existing hospitalization,
 - ii. persistent or significant disability/incapacity,
 - iii. a congenital anomaly/birth defect,
 - iv. or based upon appropriate medical judgment, may jeopardize the subject's health and may require medical or surgical intervention to prevent one of the other outcomes listed in this definition (examples of such events include allergic bronchospasm requiring intensive treatment in the emergency room or at home, blood dyscrasias or convulsions that do not result in inpatient hospitalization, or the development of drug dependency or drug abuse).

Protocol Deviation (PD): Any change in the processes or procedures of research that were not approved by amendment of an IRB-approved protocol.

